17.1 Compliance with Good Clinical Practices (GCP)

The Investigator will ensure that this study is conducted in accordance with the ethical principles that have their origins in the Declaration of Helsinki and that are consistent with GCP and applicable regulatory (local) requirements; whichever affords the greater protection to the subject.

17.2 Institutional Review Board/Independent Ethics Committee

A copy of the protocol, proposed ICF, other written subject information, and any proposed advertising material must be submitted to the IRB/IEC for written approval. A copy of the written IRB/IEC approval of the protocol and ICF must be received by Stryker Neurovascular before recruitment of subjects into the Trevo Registry. The Investigator must submit and, where necessary, obtain approval from the IRB/IEC for all subsequent protocol amendments and changes to the ICF. The Investigator must notify the IRB/IEC of SAEs per IRB/IEC procedures, UADEs occurring at the site and other SAE/UADE reports received from Stryker Neurovascular in accordance with local procedures and regulations.

The Investigator is responsible for obtaining initial IRB/IEC approval and renewal throughout the duration of the registry. Copies of the Investigator's reports and the IRB/IEC continuance of approval must be sent to Stryker Neurovascular.

17.3 Protocol Adherence

Prior to beginning the study, the Investigator must sign the Investigator Agreement and Signature page documenting his/her agreement to conduct the study in accordance with the protocol. An Investigator must not make any changes or deviate from this protocol, except to protect the life and physical well-being of a subject in an emergency. Each deviation from the protocol must be documented with the date and reason for the deviation and reported to the Stryker Neurovascular as soon as possible, and to the IRB/IEC per local guidelines and government regulations. Major and minor protocol deviations are defined within **Appendix B**.

Stryker Neurovascular will ensure that this study is conducted in compliance with GCPs and all applicable regulatory requirements.

18 Study Administration

18.1 Pre-Study Documentation Requirements

Prior to enrolling any subjects into the registry the site must complete all pre-study essential documents, and these must be confirmed to be on file with the Stryker Neurovascular, including but not limited to: CV, medical license, W-9 or W-8, and signed clinical trial agreement; IRB/EC approval of the study and the Informed Consent; and all required study training. A site initiation visit will be conducted prior to authorization to enroll. No site may begin enrolling subjects until they receive written approval from the Stryker Neurovascular.

18.2 Record Retention

The Investigator will maintain all essential registry documents and source documentation, in original format, that support the data collected on the study subjects in compliance with the ICH/GCP guidelines. Documents must be retained for 2 years or longer per local governing Regulatory guidelines after a) the last approval of marketing application or b) formal discontinuation of the clinical investigation of the product. These documents will be retained for a longer period of time by agreement with Stryker Neurovascular or in compliance with other regulatory requirements. When these documents no longer need to be maintained, it is Stryker Neurovascular's responsibility to inform the Investigator. The Investigator will take measures to ensure that these essential documents are not accidentally damaged or destroyed. If for any reason the Investigator withdraws responsibility for maintaining these essential documents, custody must be transferred to an individual who will assume responsibility. Stryker Neurovascular must receive written notification of this custodial change.

18.3 Criteria for Terminating Study

Stryker Neurovascular reserves the right to terminate the study but intends only to exercise this right for valid scientific or administrative reasons and reasons related to protection of subjects. Investigators and associated IRB/EC will be notified in writing in the event of termination.

Appendix A. Abbreviations

Abbreviation/ Acronym	Full Term
AE	Adverse Event
AHA	American Heart Association
Carotid T	Distal terminus of the carotid artery
CRA	Clinical Research Associate
CRF	Case Report Form
CSA	Clinical Study Agreement
CT	Computed Tomography
CTA	Computed Tomography Angiography
DRSAE	Device-related SAE
eCRF	electronic Case Report Form
GCP	Good Clinical Practices
IA	Intra-Arterial
ICH	Intracranial Hemorrhage
ID	Identification
IFU	Instructions For Use
IV	Intravenous
IV tPA	Intravenous tissue Plasminogen Activator
LAR	Legally Authorized Representative
MR	Magnetic Resonance
MRI	Magnetic Resonance Imaging
mRS	Modified Rankin Scale
PI	Principal Investigator
SAE	Serious Adverse Event
SADE	Serious Adverse Device Effect
SAH	Subarachnoid Hemorrhage

STRYKER CONFIDENTIAL - THIS DOCUMENT CONTAINS CONFIDENTIAL AND PROPRIETARY INFORMATION THAT IS THE PROPERTY OF STRYKER CORPORATION. NEITHER THIS DOCUMENT NOR THE INFORMATION HEREIN MAY BE REPRODUCED, USED, OR DISCLOSED TO ANY THIRD PARTY WITHOUT THE PRIOR WRITTEN CONSENT OF STRYKER CORPORATION.

CDM 1000023 Rev. AC

Trevo[®] Retriever Registry

SBP	Systolic Blood Pressure
SICH	Symptomatic Intracranial Hemorrhage
TICI	(modified) Thrombolysis in Cerebral Infarction
t-PA	Tissue Plasminogen Activator
UADE	Unanticipated Adverse Device Effect

STRYKER CONFIDENTIAL - THIS DOCUMENT CONTAINS CONFIDENTIAL AND PROPRIETARY INFORMATION THAT IS THE PROPERTY OF STRYKER CORPORATION. NEITHER THIS DOCUMENT NOR THE INFORMATION HEREIN MAY BE REPRODUCED, USED, OR DISCLOSED TO ANY THIRD PARTY WITHOUT THE PRIOR WRITTEN CONSENT OF STRYKER CORPORATION.

CDM 1000023 Rev. AC

Trevo[®] Retriever Registry

Appendix B. Definitions

Adverse Event (AE):	Any unintended disease or injury or untoward clinical sign in a research subject. NOTE - This definition does not imply that there is a relationship between the adverse event and the device under investigation.
Device Malfunction/Nonconformity:	The failure of a device to meet its performance specifications or otherwise perform as intended. Performance specifications include all claims made in the labeling for the device. The intended performance of a device refers to the intended use for which the device is labeled or marketed.
Device-Related Serious Adverse Event (DRSAE):	Trevo device related vascular perforation or intramural arterial dissection, symptomatic ICH, embolization to a new territory, intra-procedural death, or device failure (in vivo breakage).
Distal Embolization (DE):	Any downstream occlusion distal to the target artery lesion, into the target ischemic territory, is considered DE unless complete angiogram or pre procedure non-invasive imaging demonstrated patency of these distal branches.
Embolization to New Territory:	Embolization into a previously uninvolved area of the brain, e.g. ACA embolization during MCA-M1 thrombectomy procedure.
Good Clinical Outcome:	A measure of neurologic functional outcome with a score of 0–2 on the modified Rankin Scale (mRS), usually assessed 90 days after treatment.
Irreversible Neurological Deterioration:	Neurological deterioration that is more than transitory, and is not related only to sedation. The neurological deterioration persists even after removal of sedation.
Modified Rankin Scale (mRS):	Scale for measuring the degree of disability or dependence in the daily activities of people who have suffered a stroke or other causes of neurological disability.
NIHSS Scale:	An assessment to objectively quantify the impairment caused by a stroke. It is composed of 11 items, each of which scores a specific ability between a 0 and 4. For each item, a score of 0 typically indicates normal function in that specific ability, while a higher score is indicative of some level of impairment. The individual scores from each item are summed in order to calculate a subject's total NIHSS score. The maximum possible score is 42, with the minimum score being a 0.
Pre-stroke disability:	Obtained at baseline, is representative of the subject's status before the index stroke, assessed by mRS on medical history obtained from subject, medical chart, or family members.
Procedure-Related Serious Adverse Event (PRSAE):	Procedure-related events that include, but are not limited to vascular perforation or intramural arterial dissection, symptomatic ICH, embolization to a new territory, or access site complication requiring surgical repair or blood transfusion, intra-procedural death, or device failure (e.g. in vivo breakage).

STRYKER CONFIDENTIAL - THIS DOCUMENT CONTAINS CONFIDENTIAL AND PROPRIETARY INFORMATION THAT IS THE PROPERTY OF STRYKER CORPORATION. NEITHER THIS DOCUMENT NOR THE INFORMATION HEREIN MAY BE REPRODUCED, USED, OR DISCLOSED TO ANY THIRD PARTY WITHOUT THE PRIOR WRITTEN CONSENT OF STRYKER CORPORATION.
CDM 1000023 Rev. AC

Trevo[®] Retriever Registry

Protocol Deviation:	This protocol does not require specific interventions, therefore the term deviation will only be used to describe the following situation: Failure to obtain informed consent per Good Clinical Practices (GCP).
Serious Adverse Device Effect (SADE):	An adverse device effect that has resulted in any of the consequences characteristic of a serious adverse event or that might have led to any of these consequences if suitable action had not been taken or if circumstances had been less fortunate.
Serious Adverse Event (SAE):	An adverse event in a research subject that led to a death, or led to a serious deterioration in the health of the subject that resulted in a life-threatening illness or injury, or resulted in a permanent impairment of a body structure or a body function, or required in-subject hospitalization or prolongation of existing hospitalization, or resulted in medical or surgical intervention to prevent permanent impairment to body structure or a body function. SAEs are a subset of AEs.
Subarachnoid Hemorrhage (SAH):	Bleeding into the subarachnoid space - the area between the arachnoid membrane and the pia mater surrounding the brain.
Symptomatic ICH (SICH):	The primary protocol definition is adapted from ECASS III as any apparently extravascular blood in the brain or within the cranium that is associated with clinical deterioration as defined by an increase of four points or more in the NIHSS or that led to death and was judged to be the predominant cause of a neurologic deterioration. SITS-MOST definition is any PH-2, defined as dense hematoma > 30% total of the infarcted area with substantial space-occupying effect or any hemorrhage area outside the infarcted area.

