5.2 Secondary Data points

- a. Day 90 mRS (good clinical outcomes defined as mRS of 0-2)
- b. Day 90 mortality
- c. Neurological deterioration at 24 hours, defined as a four or more point increase in the NIHSS score from the baseline score
- d. Rates of device and procedure related serious AEs

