It is important that the Investigator and relevant study site personnel are available during monitoring visits and that sufficient time is devoted to the process. In order to perform her or his role well, the monitor must be given access to primary subject medical records which support the registry eCRFs. This access must be disclosed to the subject via the informed consent.

The investigator agrees to complete all registry requirements within three months of written notice of enrollment completion. Continuation of the registry beyond this time must be mutually agreed upon in writing by both the investigator and Stryker Neurovascular.

Stryker Neurovascular will conduct a registry closeout meeting with each Trevo Registry site after the final data query is generated and data requests are addressed. The purpose of the closeout meeting is to confirm that all registry-related activities are complete and site personnel are aware of the regulatory obligations following study closure activities. The closeout meeting may transpire remotely e.g. teleconference or at an on-site monitoring visit. The closeout activities include but are not limited to the following:

- Final regulatory document review and collection of any outstanding documents including a copy of the investigator notification letter sent to the IRB/EC regarding completion of the Trevo Retriever Registry
- Address and close any open action items
- Discuss record retention requirements
- Review publication guidelines

12 Auditing

Sites may be subject to a quality assurance audit by Stryker Neurovascular or its designees, or other regulatory authorities.

Trevo[®] Retriever Registry

It is important that the Investigator and relevant study personnel are available during any audits and that sufficient time is devoted to the process.

13 Device Accountability

There will be no device accountability or tracking as the Trevo Retriever has regulatory authorization to market the device.

14 Adverse Events

The following adverse events will be reported:

- all adverse events that occur during the procedure
- all SAEs related to the device or the procedure through Day 90
- all adverse events that result in death through Day 90

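### The distal embolization definition excludes new occlusions in branches already shown open, includes occlusions already present at baseline, and leaves the former without a clear category

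*Protocol*

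**What the plan says.** Appendix B of the protocol defines DE in one sentence with a base rule and an exception. The base rule is broad: "Any downstream occlusion distal to the target artery lesion, into the target ischemic territory, is considered DE". The exception follows at once, so that such an occlusion "is considered DE unless complete angiogram or pre procedure non-invasive imaging demonstrated patency of these distal branches".

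The next entry in the same appendix, ENT, reads: "Embolization into a previously uninvolved area of the brain, e.g. ACA embolization during MCA-M1 thrombectomy procedure".

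The two serious event definitions in Appendix B treat these categories differently. The device-related definition (DRSAE) is a closed list that includes "symptomatic ICH, embolization to a new territory, intra-procedural death, or device failure" and does not name DE. The procedure-related definition (PRSAE) also names ENT and not DE, but its list is open: "Procedure-related events that include, but are not limited to vascular perforation or intramural arterial dissection".

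Section 5.2 lists as secondary data point (d): "Rates of device and procedure related serious AEs". Section 14 requires reporting of "all adverse events that occur during the procedure", together with device- or procedure-related serious events and fatal events through Day 90.

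**The concern.** A definition of embolization should separate occlusions that appeared during the procedure from those already there. Evidence that a branch was open beforehand is the best evidence that a later occlusion in it is new. The DE entry uses that evidence as the reason not to call the event DE.

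The classification is made when the event is recorded, so it cannot be left to the analysis. The Synopsis allows up to 100 sites, Section 14.2 leaves relationship to the investigator, and Section 5.3 says only that images may go to a core lab. Section 2.1 describes a clinical events committee that adjudicated events in the earlier TREVO study; the protocol describes none for this registry. The written definition is therefore the main control on consistency between sites. Section 6 gives safety monitoring and the detection of rare complications among the registry's purposes, so embolic events matter to it.

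**Working it through.** No arithmetic applies, and the plan has no figure to reproduce. The check applies the DE sentence literally to an occlusion beyond the target lesion and inside the treated territory, under each possible state of prior imaging.

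1. **Branch shown open beforehand.** The occlusion is new. The exception applies, so the event is not DE.
2. **Branch shown occluded beforehand.** The occlusion is old. The exception does not apply, so the event is DE.
3. **Branch status not shown beforehand.** The origin is uncertain. The exception does not apply, so the event is DE.

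The exception removes the only state in which imaging proves a new occlusion and keeps the state in which imaging proves an old one. Counting state 3 can be defended as a cautious default; states 1 and 2 are the problem.

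Reading the complete angiogram as the end-of-procedure run does not help. A branch that is open on that run is not an occlusion, so the exception would have nothing to act on.

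Next, does ENT catch state 1? ENT needs an area of brain not previously involved, and its example is the territory of a different artery. The DE entry concerns branches inside the target ischemic territory. No sentence sends an event excluded from DE to ENT, and no other section restates or corrects either entry. State 1 therefore has no clear category.

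Last, where does the label matter?

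- **Primary data point (Section 5.1):** modified TICI at the end of the procedure. DE plays no part.
- **Secondary and other data points (Sections 5.2 and 5.3):** DE is not named.
- **DRSAE (Appendix B):** names ENT, does not name DE, closed list.
- **PRSAE (Appendix B):** names ENT, does not name DE, open list.
- **Reporting (Section 14):** a procedural adverse event is reported whatever its label.

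The same state 1 event, if serious and device-related, is thus a listed DRSAE component when a site calls it ENT and is not one when the site calls it DE or neither. It can enter the PRSAE list in either case.

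**The case against.** The strongest defence is that the exception is a sorting rule. DE would be the default for occlusions of unproven origin in an already ischemic bed, and an occlusion proven new would move to ENT. The example in the ENT entry is only an example, and a branch shown open could be called previously uninvolved. Since ENT is named in both serious event definitions, this would be the cautious choice for safety. The reading is possible, but the link is not written, and it sits badly with a DE entry that speaks of branches within the target territory. It also leaves state 2 unrepaired: an occlusion already present at baseline would still be DE. What stands is that the sponsor's intention cannot be read from the text, so simply reversing the exception would be a guess. Reversal alone would also put proven emboli in a category that the DRSAE list does not name.

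The second defence is that DE feeds no listed endpoint and that events are captured anyway. That is right, and it limits the point. A reader might infer that proven emboli vanish from safety reporting. The documents do not support this: Section 14 captures all procedural adverse events, Section 14.1 defines seriousness by consequence and not by label, and the PRSAE list is open. A reader might also infer that the registry's embolization results become meaningless. That does not follow, because ENT in a clearly separate territory is unaffected.

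**Conclusion.** The concern holds as a misclassification in a stated safety definition. Followed literally, Appendix B leaves a new occlusion in a proven-open branch of the target territory outside DE and not clearly inside ENT, and it counts a baseline occlusion as DE.

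Its reach is limited to any DE rate that is reported and to whether such an event is a listed DRSAE component for data point 5.2(d). The second effect assumes that the Appendix B list governs the count in 5.2(d); if investigator-assessed relationship under Section 14.2 governs it instead, the effect is smaller. The primary data point is unaffected.

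No number of affected events can be given. The protocol has no DE rate. The nearest figure, 6.8% (6/88) for Trevo in TREVO 2 (Section 2.2), is for embolization to uninvolved territory, which is a different event. The direction of change is also unknown: removing baseline occlusions lowers the DE count, while placing proven-new occlusions in DE raises it. The point is worth correcting because the rule misleads when followed and the correction is small.

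**What to change.** Reconcile the DE and ENT entries in Appendix B so that every new occlusion falls in exactly one category:

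- Except from DE the branches that pre-procedure imaging or the baseline angiogram showed to be already occluded.
- State whether a new occlusion in a target-territory branch that was shown open is DE or ENT.
- If it is ENT, say so in the ENT entry.
- If it is DE, say whether a serious device-related DE counts as a DRSAE.
- Align the eCRF help text with the revised entries.

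The cost is a short wording change in the appendix and the matching help text. Recorded DE, ENT or DRSAE rates may shift, so events classified before and after the change should not be pooled without checking how the earlier ones were labelled.

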Appendix D. Time and Events Schedule

Time and Events Schedule						
Assessments:	Pre-procedure (Screening /Baseline)	Procedure	24 (-6/+24) hrs post procedure	Discharge (or Day 5-7 whichever comes first)	Day 30 +14 days	Day 90*** ±14 days
Inclusion/Exclusion Criteria	✓					
Informed Consent*	✓					
Demographics and Medical History	✓					
Baseline Medications	✓					
Baseline Labs (PT, PTT platelets, INR, glucose). Pregnancy test, if applicable	✓					
mRS**	✓			✓	✓	✓
NIHSS assessment	✓		✓	✓		
Stroke onset/etiology	✓			✓		
CT/MR‡	✓		✓			
Angiogram Procedure Information †****‡		✓				
Hospital Stay/Discharge Disposition				✓		
Post Discharge Follow-up****					✓	✓
Adverse Events†		✓	✓	✓	✓	✓
Utilization/Economic measures‡‡				✓		✓
Study Completion						✓

*Written IC must be obtained prior to any data entry.
 **Telephone mRS assessment is acceptable if subject not able to return to the clinic in person.
 ***See study binder for worksheets listing items to record during the procedure.
 ****Study Staff should review the study requirements with the subject and arrange all follow-up visits at discharge.
 † All AE during procedure and only DR and PR SAE, death post procedure.
 ‡‡De-identify forms and enter subject ID # prior to sending to Stryker
 ‡ CT/MR and Angiographic images will be de-identified with subject ID# if submitted to SNV or the core lab.

STRYKER CONFIDENTIAL - THIS DOCUMENT CONTAINS CONFIDENTIAL AND PROPRIETARY INFORMATION THAT IS THE PROPERTY OF STRYKER CORPORATION. NEITHER THIS DOCUMENT NOR THE INFORMATION HEREIN MAY BE REPRODUCED, USED, OR DISCLOSED TO ANY THIRD PARTY WITHOUT THE PRIOR WRITTEN CONSENT OF STRYKER CORPORATION. CDM 10000023 Rev. AC

Trevo[®] Retriever Registry

Appendix E. Modified TIC1 Perfusion Categories

Grade 0: No Perfusion. No antegrade flow beyond the point of occlusion.

Grade 1: Penetration with Minimal Perfusion. The contrast material passes beyond the area of obstruction but fails to opacify the entire cerebral bed distal to the obstruction for the duration of the angiographic run.

Grade 2: Partial Perfusion. The contrast material passes beyond the obstruction and opacifies the arterial bed distal to the obstruction. However, the rate of entry of contrast into the vessel distal to the obstruction and/or its rate of clearance from the distal bed are perceptibly slower than its entry into and/or clearance from comparable areas not perfused by the previously occluded vessel, e.g. the opposite cerebral artery or the arterial bed proximal to the obstruction.

Grade 2a: Partial filling with <50% of the entire vascular territory is visualized.

Grade 2b: Partial filling with \geq 50% of the entire vascular territory is visualized. If complete filling of all of the expected vascular territory is visualized, the filling is slower than normal.

Grade 3: Complete Perfusion. Antegrade flow into the bed distal to the obstruction occurs as promptly as into the obstruction and clearance of contrast material from the involved bed is as rapid as from an uninvolved other bed of the same vessel or the opposite cerebral artery.

Reference

Trevo[®] Retriever Registry

